We propose to develop and standardize a test which can reliably detect the BRAFV600E mutation in patients with known tissue BRAFV600E mutation in the blood of patients with melanoma. We aim to correlate testing with worse clinical outcome when disease is resected and to correlate blood testing with disease response to MAPK pathway inhibitors in the advanced, as well as potentially the adjuvant, setting.

### **3. PARTICIPANT SELECTION**

Participants must meet the following criteria on screening examination to be eligible to participate in the study:

#### **3.1 Eligibility Criteria**

- 3.1.1 All participants must have biopsy-proven advanced (unresectable stage IIIC or Stage IV) or high-risk (Stage II or Stage III) malignant melanoma
- 3.1.2 Participants must be 18 years of age or older
- 3.1.3 Participant must have the ability to understand and willingness to sign a written informed consent document

### **3.2 Exclusion Criteria**

3.2.1 Participants with a history of different malignancy are ineligible except for the following circumstances.

- Non-metastatic prostate cancer, cervical cancer *in situ*, and basal cell or squamous cell carcinoma of the skin.
- Individuals with a history of other malignancies are eligible if they have been disease-free for at least 2 years and are deemed by the investigator to be at low risk for recurrence of that malignancy.

3.2.2 Participants with a known history of a different BRAF-mutant malignancy

### **3.3 Inclusion of Women and Minorities**

Both men and women of all races and ethnic groups are eligible for this trial

## **4. REGISTRATION PROCEDURES**

Participation is strictly voluntary. Patients coming to the participating sites that meet the eligibility criteria will be identified by physicians, study coordinator, research nurse, or other study team member. Potential participants will receive a description of the study, including the nature of participation, and the phone numbers for study contacts. Participants may be enrolled prospectively or retrospectively.

Written informed consent will be obtained by a physician or other licensed study team member prior to enrollment into the study. All participants (except those who have previously signed consent to enroll in either the 02-017 or 11-181 protocols) must be provided a consent form describing this study and providing sufficient information for participants to make an informed decision about their participation in this study. Study coordinators will be allowed to obtain consent, as outlined in the November 2014 Guide to Human Research Activities, after receiving training from the principal investigator or by a sub-investigator following approval by the principal investigator.

The formal consent of a participant, using the IRB approved consent form, must be obtained before the participant is involved in any study-related procedure. The consent form must be signed and dated by the participant or the participant's legally authorized representative, and by the person obtaining the consent. The participant must be given a copy of the signed and dated consent document. The original signed copy of the consent document must be retained in the medical record or research file.

This study has minimal to no risk to the study participants.

#### 4.1 General Guidelines for DF/HCC Institutions

Institutions will register eligible participants in the Clinical Trials Management System (CTMS) OnCore. Registration must occur within 24 hours of the first blood sample being drawn. Any participant not consented to the protocol before protocol therapy begins will be considered ineligible and registration will be denied.

An investigator will confirm eligibility criteria and a member of the study team will complete the protocol-specific eligibility checklist.

Following registration, participants may continue protocol interventions. If a participant does not receive protocol interventions following registration, the participant's registration on the study must be canceled. Registration cancellations must be made in OnCore as soon as possible.

#### 4.2 Registration Process for DF/HCC Institutions

DF/HCC Standard Operating Procedure for Human Subject Research Titled *Subject Protocol Registration* (SOP #: REGIST-101) must be followed.

#### 4.3 General Guidelines for Other Investigative Sites

Not Applicable.

#### 4.4 Registration Process for Other Investigative Sites

Not Applicable.

### 5. STUDY DESIGN

#### 5.1 Sample Collection

##### Advanced Disease Cohort:

Blood samples will be obtained on participants following signed informed consent. For patients in the advanced melanoma cohort, a one-time blood sample will be obtained prior to the commencement of systemic therapy at a time when standard-of-care blood will be drawn. While it is ideal to obtain samples prior to any systemic therapy, participants who have previously received therapy, have progressed, and are in need of additional therapy will be considered suitable for participation. Participants with known BRAF mutation (determined by standard of care tissue testing) will undergo blood draws every 4 weeks (+/- 1 week) and at the time of disease progression.

**BRAF WT (tissue):** One- time, pre-treatment blood draw

**BRAF Mut (tissue):** Pre-treatment blood draw then every 4 weeks (+/- 1 week). A

blood draw at time of progression will also be obtained.

### Stage II/ III Disease Cohort:

Blood samples will be obtained on participants following signed informed consent. For patients in the high-risk stage II/III cohort, a blood draw will be performed 4-8 weeks after the completion of surgical management at the time of standard of care blood work. In participants who sign informed consent prior to definite surgical management, a pre-operative blood draw may be obtained at the time that standard of care pre-op blood work is performed. Blood samples will then be obtained every three months following the initiation of either adjuvant therapy or routine, close follow-up for up to two years.

**Pre-op consent:** Pre-op blood draw, 4-8 week post-op blood draw, then every 3 month blood draw following initiation of adjuvant therapy/ observation for up to 2 years.

**No pre-op consent:** 4-8 week post-op blood draw, then every 3 month blood draw following initiation of adjuvant therapy/observation for up to 2 years.

Of note, retrospective samples will be analyzed in participants who have previously signed informed consent to the melanoma tissue banking protocols, DFHCC study 02-017 and 11-181. These participants will not need to sign the consent form accompanying this protocol.

## **5.2 Data Collection**

The sources of the data will be hospital/electronic medical records provided by the BIDMC Caregroup and Partners networks. Participants will be enrolled prospectively as part of the evaluation for the use of BRAFV600E specific inhibitors either for experimental protocols or as standard of care (assuming the FDA-approval of one or more of these agents) in patients with melanoma. Data regarding response, progression, and survival either will be collected as part of the study and be made accessible to the study team or will be collected as part of routine clinical care in patients treated with standard of care BRAF inhibitors.

The data collected will be demographic data (age, gender, vital status), coded encounter data (diagnoses, dates), and clinic/office notes. The records will be reviewed electronically through the online medical record system at the three institutions accessed by the study team. The team will use a password protected computer and online medical record system maintained by the BIDMC, DFCI, and MGH. All study team members have HIPAA, confidentiality, and CITI training provided by the BIDMC, DFCI, and MGH at hiring.

The database is also stored in a password protected computer at the MGH. Identifiable information to researchers will not be released outside the MGH study team. Unlinked information will be accessible through a password protected computer and database. After the data is retrieved from patient records, the results will be entered into the database unlinked to any protected health information. Any analyses, reports, or presentations of the data will not reveal

patient information. No risks are involved for individuals whose information will be used in this study. Private/confidential information will be available only to the study coordinator and the study team on the front sheet.

### **5.3 Criteria for Taking a Participant Off Study**

Participants will be removed from study when any of the following criteria apply:

- Lost to follow-up
- Withdrawal of consent for data submission
- Death

Participants will be removed from study if they request to do so. The reason for taking a participant off study, and the date the participant was removed, must be documented in the case report form (CRF).

For Centralized Subject Registrations, the research team submits a completed Off Treatment/Off Study form to ODQ when a participant comes off study. This form can be found on the ODQ website or obtained from the ODQ registration staff.

For Decentralized Subject Registrations, the research team updates the relevant Off Treatment/Off Study information in OnCore.

### **5.4 Duration of Follow Up**

Patients will be followed until disease recurrence, death, or until closure of the study. It is estimated that this study will remain open for five years.

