
Obuchowski NA. Sample size calculations in studies of test accuracy. *Stat Methods in Medical Res* 1998; 7: 371-392.

	0.90	0.95	0.95	(0.87 to 0.98)
0.6	0.80	0.90	0.92	(0.85 to 0.96)
	0.90	0.95	0.96	(0.90 to 0.99)

The cohort of patients with Stage II and resectable Stage III melanoma is an exploratory cohort. We cannot predict the sensitivity and specificity of the assay in patients with Stage II or resected Stage III disease. In addition, only patients in this cohort with T4 disease or macrometastatic lymph nodes will have adequate tissue for assessment. However, we believe it is important to include this cohort since the ability to detect BRAF in this patient population may provide a basis for proposing further studies correlating BRAF detection with disease recurrence. The sensitivity and specificity of the assay will be calculated and presented with 90% joint confidence regions. Based upon a cohort size of 110 patients, the joint confidence regions for the sensitivity and specificity will be no wider than  $\pm 0.13$ .

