## **2. To investigate the prognostic and predictive ability of peripheral blood BRAFV600 mutational testing in patients with Stage II or resectable Stage III melanoma.**

The investigation of the prognostic and predictive ability of the assay will be based on the cohort of patients with Stage II and resected Stage III disease. Some of these patients will have a tissue-based BRAF assessment and a pre-treatment blood-based BRAF assay, and some of the patients will have the blood-based assay only.

We would expect that 50% of the cohort would have BRAF-mutated disease and that 90% of those patients will have follow-up data from which to assess the predictive ability of the assay. This results in a sample of size 50. BRAF status will be classified as positive or negative based on the post-resection, blood-based assay, and where applicable, for the tissue-based assessment.

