### Prognostic Ability of the Assay

Baseline assay results will be categorized as positive or negative and also be described on a continuous scale. The proportion of patients with a positive baseline assay will be presented with a 90% exact binomial confidence interval. Based on a cohort size of 50, the confidence interval will be no wider than 0.25. Confidence intervals will also be presented for the subgroups of patients with intermediate- or high-risk disease. We will also summarize continuous baseline assay levels using descriptive statistics for the complete cohort and according to subgroups.

Preliminary assessments of prognostic ability will be conducted using Kaplan-Meier (K-M) product-limit estimates for relapse or survival and stratified log-rank tests. K-M estimates will be stratified by AJCC stage and assay results to explore assay performance across different prognostic groups. Relapse-free survival and overall survival estimates at pre-specified time points will be presented with 90% confidence intervals estimated using log(-log(survival)) methodology. A secondary analysis will be conducted in the cohort with blood- and tissue-based assessments according to the four groups defined by their combined positive/negative status to look for differences in prognosis.

The relative effect of the blood-based assay with respect to relapse or survival will be estimated using Cox regression models. Since the AJCC staging incorporates prognostic factors such as number of involved nodes, tumor burden, ulceration, and tumor thickness, the Cox models will be stratified by AJCC stage to allow for differences in the baseline hazard of relapse or death. Models will include as covariates age, site of the primary melanoma, sex, and baseline serum LDH in addition to the blood-assay results. We will use aggregated data for the primary models; secondary models will be fit separately for the intermediate- and higher-risk cohorts. Hazard ratios for the assay will be presented with 90% confidence intervals.

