### Predictive Ability of the Assay

The behavior of the blood-based assay over time will be summarized graphically by AJCC stage or according to melanoma treatment. The status of the assay will be shown at each assessment time for each patient, in addition to time of disease progression. Of particular note will be assessment times where a previously undetectable assay becomes detectable, or times where there is a doubling in the assay relative to baseline. Treatment will be classified into four groups: immunotherapy, BRAF/MEK inhibitors, other translational signal transduction/targeted therapies, or chemotherapy (cytotoxic therapy).

The first assessment of assay performance over time will take place at 3 months and will be based on fold-changes in the quantified assay relative to baseline. This early look will minimize the number of patients lost due to rapid progression of disease. Based on 18-month progression rates reported in the literature, we estimate that approximately 11% of patients will have progressed by the time of the 3-month assessment. For an initial cohort size of 50 patients, and assuming that 45 patients will have 3-month assay, a Wilcoxon-signed-rank test, comparing the observed fold-change with one, with a two-sided type-I error of 10%, will have 80% power to detect a difference in fold-change that is 0.41 times the standard deviation.

In more exploratory analyses, we will model the behavior of the assay over time using repeated measures, random-effects regression with the continuous assay measure as the dependent variable. Models will include as covariates AJCC stage and treatment classification, in addition to other prognostic factors. To investigate the relationship between the assay and PFS (or OS), we will use the extended Cox (EC) model with assay performance as the time-dependent covariate. Models will be stratified by AJCC stage, and will include treatment group and prognostic factors as predictors. In separate EC models, the assay will be modeled (a) on a continuous scale, (b) based on fold-changes from baseline, and (c) based on an indicator of assay response (double the baseline level or change from non-detectable to detectable).

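### Follow-up is said to end at recurrence, yet overall survival is analysed and no censoring rule for it is given

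*Combined protocol and SAP*

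**What the plan says.** Section 5.4 is the only statement of follow-up duration: "Patients will be followed until disease recurrence, death, or until closure of the study". It adds that the study is expected to stay open for five years.

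Other sections point the other way or depend on longer follow-up:

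- **Section 5.2** lists vital status among the items taken from the medical record, with no end date: "The data collected will be demographic data (age, gender, vital status". It also says that survival data will be collected, in a sentence worded partly around patients on BRAF inhibitors.
- **Section 5.3** opens with "Participants will be removed from study when any of the following criteria apply" and lists loss to follow-up, withdrawal of consent for data submission, and death. A participant may also ask to leave. Recurrence is not on the list.
- **Section 9.1, Prognostic Ability of the Assay**, plans Kaplan-Meier, stratified log-rank and Cox analyses of relapse or survival, and says "Relapse-free survival and overall survival estimates at pre-specified time points will be presented with 90% confidence intervals".
- **Section 9.1, Predictive Ability of the Assay**, says "To investigate the relationship between the assay and PFS (or OS), we will use the extended Cox (EC) model", with the assay as a time-dependent covariate.

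No passage defines the censoring date for OS, gives a data cut-off for it, or says that follow-up for death continues after recurrence.

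**The concern.** In resected melanoma most deaths would be expected to follow a recurrence. If follow-up stops at recurrence, those deaths are never seen. Each relapsed patient leaves the OS risk set just as the hazard of death rises, so the censoring is informative. The OS curve then describes only death without prior recurrence, and an assay that predicts relapse, and through it death, would show little or no association with OS.

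Whether this happens depends on which passage the study team follows. The records come from three institutions, and the two readings could even be mixed in one dataset.

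**Working it through.** **The passages side by side.** Under 5.4 a patient's data end at the earliest of recurrence, death and study closure. Under 5.3 recurrence does not take a patient off study, and under 5.2 vital status is collected without a stated stop. Section 9.1 needs the date of death or the date last known alive for every patient, including those who relapsed. That need is met under 5.2 and 5.3 but not under 5.4, and nothing in the text says which prevails.

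**Figures in the plan.** The plan gives no event count or power for OS, so there is no OS figure to reproduce. Two related figures agree with the plan: 110 × 0.5 × 0.9 = 49.5 (stated as 50), and 50 × 0.89 = 44.5 (stated as 45).

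**Size if 5.4 governs (illustration).**

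*Input from the plan:* "we estimate that approximately 11% of patients will have progressed by the time of the 3-month assessment". As a constant hazard, λ = −ln(0.89)/3 = 0.0388 per month. This gives 1 − 0.89^6 = 0.503 relapsed by 18 months and 1 − 0.89^12 = 0.753 by 36 months.

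*Assumed, not in the documents:* median survival after relapse of 9 to 36 months (hazard ν = ln 2/median); non-relapse death of 0.5 to 2% per year (hazard μ), acting before and after relapse; a 36-month horizon; all 50 patients observed to it.

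*Formulas,* three states (disease-free, relapsed, dead), exponential times:

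- True OS: S(t) = e^(−μt) × [e^(−λt) + λ/(λ−ν) × (e^(−νt) − e^(−λt))]
- Kaplan-Meier OS censored at relapse: e^(−μt)
- Probability of a counted death: C(t) = μ/(λ+μ) × (1 − e^(−(λ+μ)t))

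*Worked case, median 9 months and 2% per year:* ν = 0.0770, μ = −ln(0.98)/12 = 0.00168, e^(−36λ) = 0.247, e^(−36ν) = 0.0625. The bracket is 0.247 + (−1.017)(0.0625 − 0.247) = 0.435. S(36) = 0.98^3 × 0.435 = 0.941 × 0.435 = 0.409. Deaths are 50 × (1 − 0.409) = 29.5, of which 50 × C(36) = 1.59 are counted, so 1 − 1.59/29.5 = 95% are missed.

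| Post-relapse median | Non-relapse death per year | True OS, 36 months | OS censored at relapse | Deaths per 50 | Counted | Missed |
|---|---|---|---|---|---|---|
| 9 months | 0.5% | 0.428 | 0.985 | 28.6 | 0.40 | 98.6% |
| 9 months | 2% | 0.409 | 0.941 | 29.5 | 1.59 | 94.6% |
| 36 months | 0.5% | 0.737 | 0.985 | 13.1 | 0.40 | 96.9% |
| 36 months | 2% | 0.705 | 0.941 | 14.8 | 1.59 | 89.2% |

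The censored estimate simply returns the assumed non-relapse death rate. It carries no information on death after melanoma relapse.

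*Falling relapse hazard.* A Weibull relapse time with shape 0.6 (assumed), anchored at 11% by 3 months, gives 29% relapsed by 18 months. Over the same four corners, true OS is 0.65 to 0.84, 8 to 18 patients die, 0.5 to 2.2 deaths are counted, and 78 to 97% are missed.

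*Hazard ratio.* A simulation of 400,000 patients assumed that a positive assay (half of patients) doubles the relapse hazard and does not affect non-relapse death. It took a 12-month median after relapse, non-relapse death of 0.001 to 0.002 per month, uniform accrual over 3 years and closure at 5 years. The OS hazard ratio was 1.75 to 1.69 with full follow-up and 1.03 with censoring at relapse. The expected value under censoring is 1, because the model gives the assay no effect on the only deaths still counted.

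**The case against.** The strongest reply is that the study team would probably read 5.4 as ending active follow-up and still take deaths from the chart. Section 5.2 names vital status and survival, and 5.3 takes patients off study at death and not at recurrence. On that reading the bias does not arise. This is a fair reading, but it has to be inferred against the only explicit rule on duration, and the survival sentence in 5.2 is partly tied to patients on BRAF inhibitors.

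Three further points reduce the weight or the size:

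- **Exploratory status.** Section 9.1 says "The cohort of patients with Stage II and resectable Stage III melanoma is an exploratory cohort", calls the Kaplan-Meier work preliminary, and attaches no power or decision to OS. This stands, and it limits how serious the point is.
- **Retrospective participants.** Sections 4 and 5.1 allow banked samples from two earlier protocols. Deaths after relapse may already be on record for these patients. Their share is not stated.
- **The numbers rest mainly on assumptions.** Only the 11% comes from the plan, and full 36-month observation is generous. With uniform accrual over 3, 4 or 5 years and closure at 5 years (assumed), the 13 to 30 observable deaths become about 12 to 28, 10 to 24 or 8 to 20. The share missed hardly moves, at 87 to 99%.

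None of this removes the contradiction or supplies the missing rule. Nor does the plan's expectation that "90% of those patients will have follow-up data from which to assess the predictive ability of the assay", since it does not say what that follow-up covers.

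**Conclusion.** The concern holds as a conflict between 5.4 and Sections 5.2, 5.3 and 9.1, together with a missing OS censoring rule. That part needs no assumption.

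The bias is conditional on 5.4 being applied literally. In that case 36-month OS is overstated by between 0.24 (0.941 − 0.705) and 0.56 (0.985 − 0.428) in the constant-hazard illustration, and most deaths are missed in every scenario, including the falling-hazard one. The exact values depend on the assumed post-relapse survival and non-relapse death rates. The direction did not change in any scenario run: OS overstated and, where a hazard ratio was computed, the assay's effect on OS pulled towards none.

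The primary sensitivity and specificity objective, relapse-free survival and the 3-month assay analysis are not affected. The point should be fixed, but it does not threaten the main purpose of the study.

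**What to change.** Reconcile 5.4 with 5.2, 5.3 and 9.1:

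1. In 5.4, state that vital status and date of death are collected for every patient after recurrence, until death, withdrawal or study closure, from the record systems named in 5.2 and with a stated data cut-off.
2. In 9.1, state that OS is censored at the date last known alive and that recurrence does not censor it.
3. If this is not feasible, remove the OS analyses and keep those based on relapse.

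The blood-draw schedule in 5.1 does not need to change.

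The cost is a short amendment with IRB approval (Section 8.3) and periodic chart review in records already in use, with no added visits or samples. Section 5.2 says results are entered unlinked to protected health information, so a link must be kept to update vital status. It should also be checked that consent covers data collection after recurrence. Deaths outside the three institutions may still be missed. Those patients would be censored at the date last known alive, so OS may stay somewhat incomplete.
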